12.4 Incidence of physical examination, vital signs

Physical examinations will consist of the following body systems: (1) general, appearance; (2) extremities; (3) skin; (4) head and neck; (5) eyes, ears, nose and throat; (6) lungs and chest; (7) heart/ cardiovascular; (8) neurological; (9) abdomen / gastrointestinal; (10) liver; (11) musculoskeletal; and (12) other. Each system should be assessed as normal or abnormal and in the last case if that is clinically relevant or not. The incidence of patients with at least one change from normal at baseline to abnormal at Visit 3 will be calculated for each of the body systems.

Potentially Clinically Significant Abnormality (PCSA) are detailed below for Vital signs:

- WEIGHT change from baseline >5%
- Number of breaths per minute <12 or >25. Percentages of patients with a normal respiratory rate (RR) at baseline and an abnormally high or low RR at Visit 3 will be summarized by treatment.

Incidences will be calculated using the number of patients in the safety population as denominator.

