# 8.4.1.6 Physical examination

Complete physical examination will be performed at screening and visit 3 (day 42) or early termination. Physical examinations will consist of the following body systems: (1) general appearance; (2) extremities; (3) skin; (4) head and neck; (5) eyes, ears, nose and throat; (6) lungs and chest; (7) heart/ cardiovascular; (8) neurological; (9) abdomen / gastrointestinal; (10) liver; (11) musculoskeletal; and (12) other. Each system should be assessed as normal or abnormal and in this last case if that is clinically relevant or not.

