# **8.4.1.7 Vital signs**

Vital signs (respiratory rate, height, weight and BMI) will be assessed at all study visits (screening, visit 2 (day 14), visit 3 (day 42) or early termination, and follow-up. Blood pressure (both systolic and diastolic and heart rate) will be assessed at the same visits but this is considered for this protocol as specific cardiovascular assessment (see later).

Amendment 04, Final Version 1.0
Protocol No.: BB-2001-201b
EudraCT No.: 2017-000877-35
Page 48 / 142

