4.1 STUDY WINDOWS

The process described here will be applied for visit re-allocation except any other approach was described in section 10 or 13 of this SAP for the corresponding statistical analysis. No re-allocation will be performed for nominal visits already provided in the clinical database (visit 1, visit 2 and visit 3). However, unscheduled visits or Early Termination visit may be used to complete any missing information not gathered in the scheduled visit 2 and visit 3, according to the table below.

Table 1: Reallocation time windows definition

Scheduled Visit Post-baseline	Target Study Day	Analysis window in study days
Visit 2 (week 2)	14	10 to 21
Visit 3 (week 6)	42	22 to 45

Unscheduled visits occurring outside of the analysis windows will not be re-allocated.

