6 ANALYSIS SETS

The safety population (SAF) will be defined as all subjects who have received at least one dose of the study treatment.

Sponsor BenevolentAI Bio

Project Code ... BB-2001-201b

The intent to treat population (ITT) will be defined as all randomized subjects who have taken at least one dose of study treatment.

The per protocol population (PP) will be defined as all subjects in the FAS who do not experience a major protocol deviation.

Protocol deviations will be defined as deviations from the procedure outlined in the protocol. Protocol deviations will be identified for each patient in the Data (blind) Review & Evaluability Determination meeting will be held prior to the treatment unblinding. They will be assessed as “minor” or “major” according to the possible impact expected on efficacy results. Minor and major protocol deviations will be fully documented in the Protocol Deviation Document prior to unblinding. Specific data sets will be produced and transferred to Biostatistics department in order to allow the appropriate definition for the Per Protocol Population.

Since the reasons for excluding patients from the analysis cannot be entirely foreseen at the time of writing the statistical analysis plan evolving trial conduct may require some further definition of patients to be excluded, at the end of the trial, but prior to unblinding.

Aspects to be considered (but not limited to) when determining the evaluability of data are as follows:

- Inclusion and exclusion criteria
- Acceptable timings for visit dates and measurements
- Compliance with treatment
- Incorrect randomization/treatment
- Concomitant therapies

As far as possible ITT principle will be guaranteed so it is not expected to have protocol deviations excluding patients from the ITT population.

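### SAP 12.4 counts physical-examination and respiratory-rate shifts only at Visit 3, so early-termination findings before Day 22 score as non-events in those two summaries

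*SAP*

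**What the plan says.** For physical examination, SAP 12.4 defines the summary as "The incidence of patients with at least one change from normal at baseline to abnormal at Visit 3", calculated for each of twelve body systems. For respiratory rate, it specifies the percentage of patients with "a normal respiratory rate (RR) at baseline and an abnormally high or low RR at Visit 3 will be summarized by treatment". The denominator rule is "Incidences will be calculated using the number of patients in the safety population as denominator", and SAP 6 defines that population as "all subjects who have received at least one dose of the study treatment".

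On collection, Protocol 8.4.1.6 states "Complete physical examination will be performed at screening and visit 3 (day 42) or early termination". Protocol 8.4.1.7 says that vital signs, which include respiratory rate, "will be assessed at all study visits (screening, visit 2 (day 14), visit 3 (day 42) or early termination, and follow-up". The Early Termination paragraph of Protocol 8.4.2 asks for the Visit 3 procedures when a subject stops early.

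SAP 4.1 treats early termination as distinct from the nominal visits. Its data may complete a missing Visit 2 if the visit falls on Days 10 to 21, or a missing Visit 3 if it falls on Days 22 to 45. The rule yields only where SAP sections 10 or 13 describe another approach. It adds: "Unscheduled visits occurring outside of the analysis windows will not be re-allocated".

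**The concern.** The examinations of early stoppers are to be done and recorded, but the counting rule has no place for them if the visit comes before Day 22. Because these subjects remain in the denominator, they are scored as having no new abnormality, which is different from being treated as missing.

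The restriction also looks unintended. Protocol 8.4.7 and 11.1.7 and SAP 11 describe these endpoints without limiting them to one visit. SAP 12.2 gives suicidal-ideation findings an any-time count, and the blood-pressure, heart-rate and ECG criteria in SAP 12.6 carry no visit limit. SAP 14 declares no change from the protocol.

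At stake is the accuracy of two descriptive summaries in a dose-finding trial. An adverse event is a listed reason for discontinuation in Protocol 8.5.2. If stopping is related to treatment, the arm with most early stoppers loses most findings.

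**Working it through.** **Which termination visits reach the Visit 3 count (SAP 4.1, Table 1)**

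- Before Day 10: no analysis window, so the visit maps to nothing.
- Days 10 to 21: the visit can fill only a missing Visit 2. SAP 12.4 has no Visit 2 summary, so the finding is not counted.
- Days 22 to 45: the visit can fill a missing Visit 3, so the finding is counted.

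SAP 12 has no allocation rule of its own and is not among the excepted sections. The sentence on visits outside the windows names only unscheduled visits. For early termination before Day 10, the point is simply that no window exists.

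**The plan's own figure**

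Protocol 8.0 plans 230 randomised for 200 completers with about 15% withdrawal. 200 × 1.15 = 230, so the figure is reproduced. Dividing instead gives 200 / 0.85 = 235.3, rounded up to 236. The difference does not matter here.

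Expected withdrawals are 230 − 200 = 30, or 0.15 × 230 = 34.5.

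**Subjects affected**

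The documents do not say when withdrawals occur. Let f be the share of withdrawals whose termination visit falls before Day 22, and assume that all of these subjects attend that visit.

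- f = 0.25, lower withdrawal count: 30 × 0.25 = 7.5 subjects. That is 7.5 / 4 = 1.9 per arm, and 7.5 / 230 = 3.3% of those randomised.
- f = 0.50: 30 × 0.50 = 15 to 34.5 × 0.50 = 17 subjects, about 4 per arm.
- f = 0.75, higher withdrawal count: 34.5 × 0.75 = 25.9 subjects. That is 25.9 / 4 = 6.5 per arm, and 25.9 / 230 = about 11% of those randomised.

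If termination visits were spread evenly over Days 1 to 41, f would be 21 / 41 = 0.51, close to the middle row.

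**Effect on a reported incidence (illustration; all rates assumed)**

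Let d be the share of the safety population whose termination visit is before Day 22, p the abnormality rate in everyone else, and q the rate in those early stoppers.

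- Reported incidence = (1 − d) × p
- Incidence with all examinations counted = (1 − d) × p + d × q
- Shortfall = d × q

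With d = 0.15 × 0.50 = 0.075 and p = 10%, the reported figure is 0.925 × 10% = 9.25%. With all examinations counted it would be:

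- q = 10%: 9.25% + 0.75% = 10.0%
- q = 20%: 9.25% + 1.5% = 10.75%
- q = 50%: 9.25% + 3.75% = 13.0%

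The shortfall is never negative, so the rule cannot raise the incidence. It differs between arms whenever d or q does.

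**Respiratory rate at Visit 2**

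This is measured in subjects who continue, but an abnormal value that is normal again at Visit 3 does not enter the specified percentage. The documents give no rate from which to size this.

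**The case against.** Several arguments on the other side carry weight.

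- **Adverse events are still captured.** A reader might infer that toxicity in early stoppers disappears from the safety reporting. It does not. Under Protocol 9.1 an unfavourable sign or clinically important finding is an adverse event, and SAP 12.1 tabulates these over the safety population without visit windows. This stands, and it limits the point to two summaries. The adverse-event tables are still not a full substitute: SAP 12.4 counts any shift to abnormal, clinically relevant or not, and Protocol 9.1.2 says that signs accompanying a diagnosis are not recorded as separate events.
- **The dose comparison.** A reader might infer that the safety comparison across doses is flattened. The events that the protocol calls dose related are insomnia, abnormal dreams, headache and nausea (Protocol 5.2). Nothing in the documents shows that these appear as body-system or respiratory-rate shifts. A bias that differs by arm is possible but not demonstrated.
- **The size.** Large gaps come from assuming a much higher rate in early stoppers. With equal rates the illustration gives 9.25% against 10.0%. The SAP also tabulates twelve body systems separately, so any lost findings are spread over rows. Termination assessments are done only where possible (Protocol 7.1), so fewer subjects may have been examined.
- **Coding of the visit.** The schedule in Protocol 18.15 uses one combined column for Visit 3 and early termination. If the database stores every termination visit as Visit 3, the early-termination loss does not occur. SAP 4.1 names the two separately and points the other way, so the SAP needs to say which applies. The Visit 2 respiratory-rate gap remains in either case.
- **Respiratory rate is not wholly ignored.** The abnormality limits themselves carry no visit restriction; only the normal-to-abnormal percentage does.
- **An any-time count is not free of bias.** Unscheduled visits may be prompted by findings (Protocol 8.4.2), and follow-up readings come 28 days after the last dose. Mixing them into one incidence would be a mistake.

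**Conclusion.** The point holds for two descriptive summaries: the physical-examination incidence and the normal-to-abnormal respiratory-rate percentage in SAP 12.4. As written, a finding at an early-termination visit before Day 22 is left out and the subject counts as a non-event. Visit 2 respiratory-rate abnormalities that resolve are also missed in that percentage.

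Roughly 8 to 26 of 230 subjects could be affected, about 2 to 6 per arm. This assumes that 25% to 75% of withdrawals occur before Day 22 and that all of these subjects attend the termination visit. How many have a new abnormality is unknown, so the size of the bias in any one row cannot be stated. Its direction can: the counts can only be too low, and by different amounts in different arms if stopping is treatment-related.

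The documents do not support the wider reading that findings are lost from safety reporting as a whole. The adverse-event tables, the weight criterion and the respiratory-rate limits are not tied to Visit 3. The conclusion also depends on the database keeping early termination separate from Visit 3, as SAP 4.1 implies.

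**What to change.** - In SAP 12.4, define the incidence for each body system and for respiratory rate as a change from normal at baseline to abnormal at any on-treatment post-baseline assessment: Visit 2 where measured, Visit 3, or Early Termination on whatever day it occurs. Name these visits explicitly, because SAP 12 gives the on-treatment period a start but no end.
- Keep the Visit 3 summary as an addition.
- Show findings from unscheduled visits and from the 28-day follow-up separately.
- In SAP 4.1, state that the re-allocation windows do not exclude assessments from these any-time safety incidences, and say how early-termination visits are coded relative to Visit 3.

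The cost is SAP wording, a little more programming and one additional table. No new data are needed.

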### 11.1.7 Safety Analyses

Adverse events, adverse events of special interest, serious adverse events, serious and related adverse events will be coded using the latest available MedDRA version and their corresponding incidences will be summarised as overall events, related events, and events by intensity. AEs will be summarised by MedDRA preferred term and system organ class (primary SOC). Summaries of AEs by preferred term and decreasing frequency and by maximum severity will also be prepared.

Physical examination changes, vital signs changes, laboratory tests changes, cardiovascular changes, ocular changes, suicidal ideation (C-SSRS) findings, and positive psychotic symptoms (BPRS+) findings will be described for the different treatment groups and assessed as either clinically or non-clinically significant findings.

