#### 18.2. UK PDS Brain Bank Diagnostic Criteria for Parkinson's Disease

# UK PARKINSON'S DISEASE SOCIETY BRAIN BANK CLINICAL DIAGNOSTIC CRITERIA\*

Step 1. Diagnosis of Parkinsonian Syndrome

- Bradykinesia
- At least one of the following
  - Muscular rigidity
  - 4-6 Hz rest tremor
- postural instability not caused by primary visual, vestibular, cerebellar, or proprioceptive dysfunction

Step 2 Exclusion criteria for Parkinson's disease

- history of repeated strokes with stepwise progression of parkinsonian features
- history of repeated head injury
- history of definite encephalitis
- oculogyric crises
- neuroleptic treatment at onset of symptoms
- more than one affected relative
- sustained remission
- strictly unilateral features after 3 years
- supranuclear gaze palsy
- cerebellar signs
- early severe autonomic involvement
- early severe dementia with disturbances of memory, language, and praxis
- Babinski sign
- presence of cerebral tumor or communication hydrocephalus on imaging study
- negative response to large doses of levodopa in absence of malabsorption
- MPTP exposure

Step 3 supportive prospective positive criteria for Parkinson's disease

Three or more required for diagnosis of definite Parkinson's disease in combination with step one

- Unilateral onset
- Rest tremor present
- Progressive disorder
- Persistent asymmetry affecting side of onset most
- Excellent response (70-100%) to levodopa
- Severe levodopa-induced chorea
- Levodopa response for 5 years or more
- Clinical course of ten years or more

\*From: Hughes AJ, Daniel SE, Kilford L, Lees AJ. Accuracy of clinical diagnosis of idiopathic Parkinson's disease. A clinico-pathological study of 100 cases. JNNP 1992;55:181-184.

Amendment 04, Final Version 1.0
Protocol No.: BB-2001-201b
EudraCT No.: 2017-000877-35
Amendment 04, Final Version 1.0
07/Nov/2018
Page 101 / 142

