11 SAFETY ENDPOINTS

The safety analysis will be based on the reported adverse events and other safety information, such as clinical laboratory data and physical examination as described in the protocol.

The safety of Bavisant compared to placebo will be assessed by the evaluation of the following:

- Incidence of Adverse Events (AEs), Serious Adverse Events (SAEs), Serious and related Adverse Events and Adverse Events of Special Interest (AESIs) headache, nausea and insomnia
- Incidence of suicidal ideation (C-SSRS) findings from screening/baseline to the end of the 2-week and the 6-week treatment period and safety follow-up
- Incidence of positive psychotic symptoms (BPRS+) findings from screening/baseline to the end of the 2-week and the 6-week treatment period and safety follow-up
- Incidence of physical examination, vital signs and laboratory tests changes from normal to abnormal (haematology and biochemistry)
- Incidence of cardiovascular safety findings (blood pressure, heart rate, ECG including QT/QTc)

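### SAP 12.4 counts a physical-examination finding only when a normal system turns abnormal, so its neurological row has a low ceiling in Parkinson's disease and a near-zero result there would not be reassuring

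*SAP*

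**What the plan says.** **The SAP.** Section 12.4 names twelve body systems, neurological among them: "8) neurological; (9) abdomen / gastrointestinal; (10) liver; (11) musculoskeletal; and (12) other". It then defines the summary as a per-patient incidence, with the event worded thus: "change from normal at baseline to abnormal at Visit 3 will be calculated for each of the body systems". The safety population is the denominator. Section 11 lists the endpoint in the same terms: "Incidence of physical examination, vital signs and laboratory tests changes from normal to abnormal". No other physical-examination summary is described. Section 14 declares no change to the protocol's statistical content.

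**The protocol.** Section 8.4.1.6 schedules the examination at screening and at Visit 3 or early termination, and asks for more than a two-way rating: "Each system should be assessed as normal or abnormal and in this last case if that is clinically relevant or not". Section 11.1.7 says that physical-examination changes will be "described for the different treatment groups and assessed as either clinically or non-clinically significant findings".

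**The population.** Inclusion criterion 3 requires a diagnosis of Parkinson's disease by the UK Brain Bank criteria. In Appendix 18.2, under "Step 1. Diagnosis of Parkinsonian Syndrome", these ask for bradykinesia together with rigidity, rest tremor or postural instability.

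**The concern.** The event needs a normal starting point. In this trial the entry diagnosis is itself made from signs that a neurological examination looks for, and the only scheduled pre-treatment physical examination comes after that diagnosis. The neurological row therefore excludes from counting the subjects who are most typical of the trial, yet keeps them in the denominator. For a drug that acts on the central nervous system, a row of very small percentages in all four arms could be taken as evidence that neurological findings are rare, when the rule itself keeps the figures small.

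A second loss is separate from the first. The protocol collects whether each abnormality is clinically relevant. SAP 12.4 repeats that grading and then does not use it, so a move from abnormal without clinical relevance to abnormal with clinical relevance is not counted. Section 11.1.7 of the protocol refers to this distinction, and SAP 14 does not mention that it has been left out.

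**Working it through.** The plan gives no figure for this endpoint, so there is none to reproduce. The check is on the logic of the rule, followed by an illustration of its size.

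**Inputs**
- Counting rule and denominator: SAP 12.4.
- Planned number: about 230 subjects, randomised 1:1:1:1 (protocol 7.1), so 230 / 4 = 57.5 per arm.
- q, the share rated neurologically abnormal at baseline: not in the documents; assumed 0.5 to 1.0.
- w, the true share who worsen neurologically: not in the documents; assumed 10% for illustration, and the same in subjects who start normal and in those who start abnormal.

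**Step 1, who can be counted.** A subject abnormal at baseline cannot make the required change. The number per arm who can be counted is 57.5 × (1 − q).

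**Step 2, ceiling.** The denominator stays the whole arm, so the reported incidence cannot exceed 1 − q.

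**Step 3, reported incidence.** Under the assumption on w, it is (1 − q) × w. With w = 10%, 57.5 × 0.10 = 5.75 subjects per arm truly worsen.

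| q (assumed) | Can be counted, per arm | Ceiling | Counted of 5.75 worsened | Reported |
|---|---|---|---|---|
| 0.50 | 28.75 | 50% | 2.88 | 5.0% |
| 0.80 | 11.50 | 20% | 1.15 | 2.0% |
| 0.90 | 5.75 | 10% | 0.58 | 1.0% |
| 0.95 | 2.88 | 5% | 0.29 | 0.5% |
| 1.00 | 0 | 0% | 0 | 0% |

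If q is similar across arms, any difference between arms shrinks by the same factor 1 − q.

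**Step 4, comparison with neighbouring sections.** Laboratory values get shift tables across below, within and above normal (SAP 12.5). BPRS+ counts patients with any increase or decrease from baseline (SAP 12.3). The blood pressure and heart rate criteria include changes from baseline whatever the starting value (SAP 12.6). The physical examination is treated more narrowly than these, and no reason is given.

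**The case against.** **Worsening has other routes.** Protocol 9.1.1 makes worsening of a condition present before treatment a new adverse event, and SAP 12.1 treats worsening as an onset. UPDRS Part III grades rigidity, tremor, bradykinesia and postural stability at baseline, week 2 and week 6, and is compared between arms (SAP 9.2.6 and 10.2). This stands. A reader might infer from SAP 12.4 that neurological worsening is captured nowhere in the trial; the documents do not support that. The other routes still do not repair this table. Under protocol 9.1.2, worsening of a degenerative condition is an adverse event only when it exceeds what would be expected, and UPDRS Part III is an efficacy mean change covering motor signs, not a safety count of subjects who worsened.

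**The baseline share is unknown.** A reader might also infer that none of the 230 subjects can be counted and that the row must show 0% in every arm. That is only the limiting case q = 1. The criterion asks for a previous diagnosis, stable Parkinson's medication is permitted, and nothing says how known signs should be rated on the screening item, so some subjects may be rated normal. This also stands, which is why the size is given as a range.

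**The protocol does not demand a shift table.** Its endpoint is the incidence of findings (6.2.2 and 8.4.7), and new abnormality is an ordinary way to define incidence. Table shells are separate documents (SAP 17) and may show more. This is fair as far as it goes, but the SAP is the governing text, and it omits a grade that protocol 11.1.7 names.

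**A three-level table may meet the same ceiling.** If disease-defining signs are graded clinically relevant at screening, no worse level exists for those subjects. This is correct, and the remedy has to say so.

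**Conclusion.** The point holds for the physical-examination summary in SAP 12.4 and its listing in SAP 11. By logic alone, a subject abnormal in a system at baseline cannot contribute an event but remains in the denominator. The neurological row is the one most exposed, because the entry diagnosis rests on neurological signs. Its ceiling is 1 − q, from 50% down to 0% over the assumed q of 0.5 to 1.0. The reported values in the table rest on the further assumption of equal worsening whatever the baseline rating. Other systems follow the same formula with their own q, about which the documents say nothing.

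A near-zero neurological row should not be read as reassurance. The omission of the clinical-relevance grade is a narrowing against protocol 11.1.7 that SAP 14 does not list. The table is descriptive and untested, so the primary result, error rate and power are unaffected. The change is still worth making before unblinding because the grade is already collected.

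**What to change.** In SAP 12.4, replace the count with a baseline-to-Visit 3 shift table for each body system, with three levels: normal; abnormal, not clinically relevant; abnormal, clinically relevant. Use subjects examined at both visits as denominator. Count any shift to a worse level as an incident finding, and show shifts to clinically relevant separately, in line with protocol 11.1.7. Align the wording in SAP 11.

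Add a footnote that worsening within the clinically relevant level is not visible in this table and should be read from the adverse events and UPDRS Part III.

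The cost is SAP wording, one more table shell and slightly more programming. No new data are needed, and the layout matches what SAP 12.5 already plans for laboratory values.
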